## Analysis of Secondary Efficacy variables

### *Tumour and specimen measures*

The specimen volume after BCL-guided partial mastectomy was determined using the water displacement method, with results recorded on the same day as the surgery (Visit V2). Summary statistics will be calculated for the specimen volume, as well as for the maximal tumor diameter on the pathology report of the lumpectomy specimen (cm). The results will be presented in tables, along with tumor volumes and the ideal specimen volume derived from preoperative imaging for comparative purposes, and box plots will be used to visualize differences and variability in volumes.

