#### 1.3.2. Secondary Objective(s)

The secondary objectives of the study are:

- To calculate the specimen volume after BCL guided partial mastectomy;
- To evaluate the surgeon's perception of ease of use of the BCL system;
- To evaluate the safety and tolerability of BCL;
- To evaluate the patient's satisfaction;
- To compare the ideal specimen volume to the actual specimen volume and tumor volume;
- To record important clinical data on the removed specimens.

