### 5.2. General Methodology and Presentation of the Results

All collected data will be presented through listings and tables.

To ensure effective presentation of results, if deemed necessary, listings shall be divided into two or more distinct outputs. Each newly created listing will maintain the original table number, followed by a consecutive alphabetical letter, and the original title; additional specifications regarding the contents of the listing may be included after the listing title.

In tables, default summary statistics for quantitative variables will be:

- Mean, Standard Deviation (SD), number of missing observations (N), minimum and maximum values, if all continuous variables of a specific section (i.e., vital signs, blood evaluation, etc.) could be considered normal;
- Median, Range Q1 - Q3, number of missing observations (N), minimum and maximum values, if at least one continuous variable of a specific section (i.e., vital signs, blood evaluation, etc.) couldn't be considered normal.

For simplicity, the mockup tables in this SAP use the first case. However, the final study report will reflect the appropriate case based on the data distribution.

For qualitative variables, the counts (N) and percentage (%) of patients with non-missing data per category will be the default summary presentation, and, where appropriate and present, the number of missing values as a "Missing" category.

Percentages will be calculated using as the denominator the number of all patients in a specified population or treatment group, unless specified otherwise. The denominator will be specified in a footnote to the tables for clarification if necessary.

All listings will be produced with reference to the set of All patients.

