#### Collected Variables:

Previous radiological assessment

- Was mammogram available prior to enrollment? (Yes/No) [CRF – V0]
- If No, please specify (free text) [CRF – V0]
- If Yes, was IBC/DCIS confirmed? (Yes/No) [CRF – V0]
- Was prone MRI available prior to enrollment? (Yes/No) [CRF – V0]
- If No, please specify (free text) [CRF – V0]
- Tumor maximal diameter (mm) (number) [CRF – V0]
- Presence of satellite lesions less than or equal to 2 cm from the primary? (Yes/No) [CRF – V0]
- Was pathological analysis of diagnostic core biopsy specimens available prior to enrollment? (Yes/No) [CRF – V0]
- If No, please specify (free text) [CRF – V0]
- If Yes, IBC or DCIS? (DCIS/IBC/Both DCIS and IBC) [CRF – V0]

Supine MRI

- Was supine MRI performed? (Yes/No) [CRF – V1]
- If No, please specify (free text) [CRF – V1]
- Where images transferred to CairnSurgical? (Yes/No) [CRF – V1]
- If no, reason (free text) [CRF – V1]
- Tumor maximum diameter (cm) (number) [CRF – V1]
- Tumor volume (cm^3) (number) [CRF – V1]
- Optimal resection volume (cm^3) (number) [CRF – V1]

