## 6.2.2. Analysis of Secondary Variables

The analysis of the following secondary endpoint will be described in this section.

The secondary endpoints are defined as follows:

- To calculate the specimen volume after BCL guided partial mastectomy, the water displacement method (WDM) will be used (results will be obtained within the same day of surgery).
- To compare the ideal specimen volume to the actual specimen volume and tumor volume, the tumor maximum diameter (mm) and tumor volume (mm^3) on supine MRI, and the ideal specimen volume (mm^3) will be recorded at V1;
- To record important clinical data on the removed specimens the presence of invasive cancer in core biopsy (Y/N), presence of DCIS in core biopsy (Y/N), presence of invasive cancer in lumpectomy specimen (Y/N), presence of DCIS in lumpectomy specimen (Y/N), subtype of invasive cancer (ductal vs lobular vs other), maximal tumor diameter (mm) on pathology report of lumpectomy specimen, shave biopsy done during surgery (Y/N and if done how many) will be recorded and checked.
- To evaluate the surgeon's perception of ease of use of the BCL system, a 5 Likert scale will be used at V2;
- To evaluate the patient's satisfaction, the BREAST-Q will be used at EOS/V4;
- To evaluate the safety and tolerability of BCL through physical examination and AEs assessment including the relationship of the AE to the BCL system at V1, V2, V3, V4.

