#### *Shave biopsies*

- Were any shave biopsies done? (Yes/No) [CRF –V2]
- If Yes, how many (number) [CRF –V2]
- What is the volume of shave biopsy determined by water displacement? (ml) (number) [CRF –V2]

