### Derived Variables:

- Breast-Q score as foreseen by the scale's user's manual.

Sum of all items scores will be calculated for both preoperative and postoperative BREAST-Q module and converted into an equivalent RASCH transformed score (0-100). Higher scores reflect a better outcome.

| MODULE        | SUM SCORE | EQUIVALENT RASCH TRANSFORMED SCORE (0-100) |
|---------------|-----------|--|
| Preoperative  | 4         | 0  |
|               | 5         | 23   |
|               | 6         | 29   |
|               | 7         | 34   |
|               | 8         | 39   |
|               | 9         | 44   |
|               | 10        | 48   |
|               | 11        | 53   |
|               | 12        | 58   |
|               | 13        | 64   |
|               | 14        | 71   |
|               | 15        | 82   |
|               | 16        | 100  |
| Postoperative | 11        | 0  |
|               | 12        | 15   |
|               | 13        | 20   |
|               | 14        | 24   |
|               | 15        | 26   |
|               | 16        | 29   |
|               | 17        | 31   |
|               | 18        | 33   |
|               | 19        | 35   |
|               | 20        | 36   |
|               | 21        | 38   |
|               | 22        | 40   |
|               | 23        | 42   |
|               | 24        | 43   |
|               | 25        | 45   |
|               | 26        | 46   |
|               | 27        | 48   |
|               | 28        | 50   |
|               | 29        | 51   |
|               | 30        | 53   |
|               | 31        | 55   |
|               | 32        | 57   |
|               | 33        | 59   |
|               | 34        | 61   |
|               | 35        | 63   |
|               | 36        | 65   |
|               | 37        | 67   |
|               | 38        | 69   |
|               | 39        | 72   |
|               | 40        | 75   |

|  |                           |                  |                |
|--|---------------------------|------------------|----------------|
|  | Form               | Form Nr.  | 1M-DMST-011-A3 |
|  | Statistical Analysis Plan | Page      | 37 of 116      |
|  |                           | Version # | 0.1            |

|  |    |     |
|--|----|-----|
|  | 41 | 78  |
|  | 42 | 82  |
|  | 43 | 88  |
|  | 44 | 100 |

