**Table 10. Previous radiological assessments**

**Safety Analysis Set**

|  |                  | SAS
(N=XX) |
|--|------------------|-----------------------|
| Mammogram available prior to enrollment?  |                  |                       |
| Yes  | N (%)            | X (XX.X)              |
| No   | N (%)            | X (XX.X)              |
| Missing  | N (%)            | X (XX.X)              |
| IBC/DCIS confirmed  |                  |                       |
| Yes  | N (%)            | X (XX.X)              |
| No   | N (%)            | X (XX.X)              |
| Missing  | N (%)            | X (XX.X)              |
| Prone MRI available prior to enrollment?  |                  |                       |
| Yes  | N (%)            | X (XX.X)              |
| No   | N (%)            | X (XX.X)              |
| Missing  | N (%)            | X (XX.X)              |
| Presence of satellite lesions less than or equal to 2 cm from the primary               |                  |                       |
| Yes  | N (%)            | X (XX.X)              |
| No   | N (%)            | X (XX.X)              |
| Missing  | N (%)            | X (XX.X)              |
| Tumor maximal diameter (cm)   | Mean ± SD | XX ± X                |
|  | Min - max | XX - X                |
|  | Missing   | X                     |
| Pathological analysis of diagnostic core biopsy specimens available prior to enrollment |                  |                       |
| Yes  | N (%)            | X (XX.X)              |
| No   | N (%)            | X (XX.X)              |
| Missing  | N (%)            | X (XX.X)              |
| If Yes, IBC or DCIS   |                  |                       |

|   |                           |                  |                |
|---|---------------------------|------------------|----------------|
|  | Form               | Form Nr.  | 1M-DMST-011-A3 |
|   | Statistical Analysis Plan | Page      | 66 of 116      |
|   |                           | Version # | 0.1            |

|  |              | SAS
(N=XX) |
|--|--------------|-----------------------|
| IBC   | N (%) | X (XX.X)              |
| DCIS  | N (%) | X (XX.X)              |
| Both  | N (%) | X (XX.X)              |
| Missing   | N (%) | X (XX.X)              |

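### The objective of comparing ideal with actual specimen volume gets only separate summaries: no per-patient difference or ratio, and shave volume is never added to the specimen

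*SAP*

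**What the plan says.** SAP 1.3.2 lists as a secondary objective "To compare the ideal specimen volume to the actual specimen volume and tumor volume". The analysis text in SAP 6.2.2 (Tumour and specimen measures) plans summary statistics for specimen volume and pathology diameter, and then says "The results will be presented in tables, along with tumor volumes and the ideal specimen volume derived from preoperative imaging for comparative purposes". Box plots are added. The layout of the table of specimen and tumor volumes in SAP 9.1 has separate mean ± SD, range and missing rows for each variable. The only derived variable in SAP 6.2.2 is the "Breast-Q score as foreseen by the scale's user's manual". Ideal and actual volume do meet on one row per patient in the listing of specimen and tumor volumes in SAP 9.2.

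Shave volume has its own CRF field ("What is the volume of shave biopsy determined by water displacement"), its own table and its own listing. No total resected volume is defined.

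Units differ between places:
- **Ideal volume.** It is in mm³ in SAP 1.2.5 and in the endpoint definition of SAP 6.2.2. In the collected variables of SAP 6.1.7 and in all outputs it is called optimal resection volume and is in cm³.
- **Supine-MRI diameter.** The endpoint definition reads "the tumor maximum diameter (mm) and tumor volume", but the diameter is collected and tabulated in cm.
- **Prone-MRI diameter.** It is collected as "Tumor maximal diameter (mm) (number" in SAP 6.1.7, but the table and listing of previous radiological assessments show it as "Tumor maximal diameter (cm". The same section says that no derived variables apply.

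SAP 5.2 replaces mean and SD by median and quartiles "if at least one continuous variable of a specific section" cannot be considered normal. Protocol 2.5.2 lists mean and median together and calls all secondary endpoints descriptive.

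**The concern.** The objective concerns individual patients: how close did each resection come to the volume planned for that breast? Two similar marginal means can coexist with large over-resection in some women and under-resection in others. The layout also counts missing values variable by variable, so the two means may not rest on the same patients.

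The definition of actual volume adds a second problem. Under protocol 2.10.2, shaves are taken only when palpation or the specimen mammogram raises doubt about a margin. The tissue left out of the comparison is therefore tissue taken where the main specimen looked insufficient. Protocol 2.11.1 anticipates an excised volume close to or below ideal, so a reader will use this table to judge that expectation.

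**Working it through.** **Plan's own figure.** The documents give no precision or sample-size figure for the volume comparison. N = 35 was chosen for the positive margin rate. The stated 15% interval width reproduces: the exact 95% limits for 1 of 35 are 0.07% and 14.92%, a width of 14.8 points, and 3% of 35 (1.05 events) gives 15.1. I take n = 35 as given.

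**Inputs.** Protocol 2.11.1 (The BCL System) gives pilot volumes of 116 + 73 ml actual and 103 + 86 ml optimal, in 19 patients with palpable tumors. I read the printed plus sign as ± SD. The within-patient correlation r is not given, so it is varied. Shave frequency and volume are not given, so they are assumed.

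**Pilot difference.** 116 − 103 = 13 ml.

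**Unpaired half-width**, as a reader would get from two separate mean ± SD rows:
SE = √((73² + 86²)/35) = √(12725/35) = 19.07 ml.
Half-width = t(68) × SE = 1.995 × 19.07 = 38.0 ml.

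**Paired half-width.** SD of the difference = √(73² + 86² − 2r × 73 × 86). Half-width = t(34) × SD/√35, with t(34) = 2.032.

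| r (assumed) | SD of difference, ml | 95% half-width, ml | Relative to 38.0 ml |
|---|---|---|---|
| 0 | 112.8 | 38.7 | 1.02 |
| 0.5 | 80.3 | 27.6 | 0.72 |
| 0.8 | 51.8 | 17.8 | 0.47 |
| 0.9 | 37.7 | 13.0 | 0.34 |

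**Shaves.** Shift in mean total volume = share of patients with shaves × mean shave volume in those patients.
- Low end: 0.20 × 5 = 1 ml.
- High end: 0.40 × 20 = 8 ml.

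If the main-specimen excess were the pilot's 13 ml, the omitted part would be 1/(13 + 1) = 7% to 8/(13 + 8) = 38% of the total excess.

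**Units.** 1 cm³ = 1 ml = 1000 mm³. Ideal volume is collected and shown in cm³ and specimen volume in ml, so the planned volume table is numerically consistent; mm³ appears only in descriptive text. Prone-MRI diameter is different. It is collected in mm and shown in cm, and with no stated conversion a 12 mm tumor could be printed as 12 cm, a factor of 10.

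**Means or medians.** A normal distribution with mean 103 and SD 86 has about 12% of its mass below zero (103/86 = 1.20 SD), which is impossible for a volume. A switch to medians for this section is therefore plausible. A difference of medians need not equal the median difference, and medians alone could not be set beside the pilot's means.

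**The case against.** The strongest reply is that the endpoint is descriptive. No test, power or confidence interval is planned for it, so no planned result becomes less precise. The patient-level listing shows the pairing, shaves have their own table and listing, and the pilot was also reported as mean against mean. This is fair on test and power, and it means that nothing is hidden. It does not settle the matter, because a paired difference is itself a descriptive statistic and is the one that the objective calls for.

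A second reply is that main-specimen volume is a defensible measure of what the device guided, since shaves are discretionary and come afterwards. That stands as a reason to keep a main-specimen row, but not as a reason to omit the total.

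A reader might infer more than the documents support:
- **Separate means bias the comparison.** They do not on complete pairs, where the difference of means equals the mean difference.
- **The mixed units corrupt the volume table.** They do not, because every field and output in that comparison is in cm³ or ml. The 10-fold hazard concerns prone-MRI diameter, which is outside the table.
- **Excess resection is understated throughout, in the device's favour.** Only total tissue removed is understated, and only in patients with shaves. If the main specimen falls short of ideal, adding shaves moves the total towards ideal.
- **Means will not be shown.** Under SAP 5.2 that is plausible but not certain.

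Finally, the SAP follows protocol V2.0, which was not supplied. The supplied protocol lacks this objective, and V2.0 may define the comparison further.

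**Conclusion.** The point holds as a gap between an objective and its analysis. The SAP sets a within-patient comparison and plans no within-patient statistic. The cost is lost precision and patient-level spread, not bias in the mean: about 38 ml half-width unpaired against 13.0 to 27.6 ml paired for correlations of 0.9 down to 0.5, with no gain at zero. These figures rest on assumed correlations and on SDs from a small pilot in palpable tumors, whereas this trial enrols non-palpable ones.

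Leaving out shaves understates total tissue removed in the patients who had them. The 1 to 8 ml shift is an illustration, because the documents give neither shave frequency nor shave volume.

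The prone-MRI diameter conflict is a separate, real reporting hazard. The mm³ wording needs reconciling but causes no error in the planned volume table. No hypothesis test or power is affected. The change should be made, but the trial's main conclusion does not depend on it.

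**What to change.** In SAP 6.2.2:
1. Derive total resected volume (ml) = specimen + all shaves. The CRF has one shave-volume field although several shaves are possible and the analysis text says each was measured, so state whether that field is a sum.
2. Derive the per-patient difference from ideal volume and the ratio to it, for main specimen alone and for the total, in patients with both values. Report each with a 95% CI from paired data, on the log scale if skewed.
3. Use one name for the planned volume (ideal or optimal) and ml (= cm³) for all volumes. Use one unit for all diameters, with any conversion listed as a derived variable in SAP 6.1.7.
4. For volumes, always show n, mean, SD, median, quartiles, minimum and maximum instead of applying the section-wide switch in SAP 5.2.

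Check the wording against protocol V2.0. The cost is a few lines of SAP text and programming and some added table rows. All data are already collected, and the supplied SAP is still version 0.1.

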### *Shave biopsies*

The number and volume of shave biopsies taken during BCL-guided partial mastectomy was recorded on the day of surgery (Visit V2). The specimen volume for each shave biopsy was determined using the water displacement method. Frequencies for the number of shave biopsies and summary statistics of their respective volumes will be calculated. (Secondary endpoint 3).

### *Cancer Characteristics in Biopsy and Lumpectomy*

Important clinical characteristics of the removed specimens will be analyzed, including the presence of invasive cancer (IBC) or ductal carcinoma in situ (DCIS) in core biopsies and lumpectomy specimens. The frequency and percentages of each classification will be summarized, along with invasive cancer subtypes (ductal, lobular, or other).

### *Surgeon's perception of ease of use of the BCL system and Visualizer*

Responses to the investigator-administered Likert questionnaire assessing the ease of use of the BCL device will be analyzed descriptively. The frequencies and percentages for each response category (e.g., "Very satisfied," "Satisfied") will be reported for all items, including overall satisfaction, ease of use, safety, reliability, and likelihood of reuse or recommendation. Results will be displayed in summary tables and listings.

The investigator's satisfaction with the Visualizer system will be analyzed using responses to a separate Likert questionnaire. Frequencies and percentages for each response will be summarized for items assessing clarity, reliability, ease of use, and the system's impact on surgical assistance and time. These results will be tabulated and listed for individual responses. (Secondary endpoint 4).

### *Patient Satisfaction (BREAST-Q Assessment)*

|   |                           |                  |                |
|---|---------------------------|------------------|----------------|
|  | Form               | Form Nr.  | 1M-DMST-011-A3 |
|   | Statistical Analysis Plan | Page      | 38 of 116      |
|   |                           | Version # | 0.1            |

Patient-reported satisfaction will be evaluated using the BREAST-Q questionnaire. The scores of each answer range from 1 (worst answer) to 4 (best answer): the raw total scores for each module (preoperative and postoperative) will be calculated, then converted to Rasch scores (0–100) as per the BREAST-Q user's manual. Higher scores reflect greater satisfaction. Missing data will be imputed with the means of completed items if less than 50% of the scale items are missing, as per the manual guidelines. Results will be summarized in tables and figures, including a box plot of Rasch scores for visual comparison.

The evaluation of the secondary endpoint related to the assessment of the safety and tolerability of BCL, including physical examination and the assessment of adverse events (AEs) — as well as the relationship between the AEs and the BCL system — will be outlined in section 6.4, Safety Variables.

### Imputations for missing values:

For breast-Q, as foreseen by scale users' manual, if missing data is less than 50% of the scale's items, the mean of the completed items will be inserted instead of the missing scores.

|                               |          |     |
|-------------------------------|----------|-----|
| Analysis Sets to be used for: | Tables   | FAS |
|                               | Listings | FAS |
|                               | Figures  | FAS |

Patients' data will be summarized as follows:

|  |   |
|--|---|
| Table 14. Specimen and tumor volumes                      | Summary statistics for specimen and tumor measurements collected at different stages of the study, including pre-surgery (Supine MRI) and post-surgery (after Surgery at V2). |
| Table 15. Shave biopsies                                  | Frequency and number of shave biopsies performed, along with the summary statistics of volume of the biopsy specimens determined by water displacement                        |
| Table 16. Cancer characteristics in biopsy and lumpectomy | Frequency of cases identified as IBC, DCIS, or both, based on core biopsy and lumpectomy specimen results, and details of subtype classifications for invasive cases.         |
| Table 17. Likert questionnaire for ease of use of BCL     | Frequencies of responses to each item on the Likert-scale questionnaire administered to the investigator regarding the ease of use of BCL.                                    |
| Table 18. Likert questionnaire the                        | Frequencies of responses to each item on the Likert-scale questionnaire administered to the investigator regarding the satisfaction towards the                               |

|  |                           |                  |                |
|--|---------------------------|------------------|----------------|
|  | Form               | Form Nr.  | 1M-DMST-011-A3 |
|  | Statistical Analysis Plan | Page      | 39 of 116      |
|  |                           | Version # | 0.1            |

Visualizer

Visualizer.

**Table 19.** Breast-Q

Frequencies of responses to all items of the BREAST-Q and summary statistics of the raw and RASCH converted score, as completed by the patients.

Patients' data will be listed as follows:

- |  |   |
|--|---|
| Listing 10. Specimen volumes                                | Listing of specimen and tumor measurements, including volumes collected pre-surgery (via supine MRI) and post-surgery (at visit V2).                        |
| Listing 11. Shave biopsies                                  | Listing of information on shave biopsies, number of shave biopsies performed, along with volume of the biopsy specimens determined by water displacement.   |
| Listing 12. Cancer characteristics in biopsy and lumpectomy | Listing of classification of cases identified as IBD, DCIS or both, and details of subtype classifications for invasive cases.                              |
| Listing 13. Likert questionnaire for ease of use of BCL     | Listing of Individual responses to all items from the Likert-scale questionnaire on the ease of use of the BCL system, as completed by investigators.       |
| Listing 14. Likert questionnaire for the Visualizer         | Listing of Individual responses to all items from the Likert-scale questionnaire on satisfaction with the Visualizer system, as completed by investigators. |
| Listing 15A. Breast-Q – pre-operative module                | Listing of Individual responses to all items from the pre-operative BREAST-Q and score, as completed by the patients.                                       |
| Listing 15B. Breast-Q – post-operative module               | Listing of Individual responses to all items from the post-operative BREAST-Q and score, as completed by the patients.                                      |

Patients' data will be represented as follows:

- |   |  |
|---|--|
| Figure 4. Tumor and specimen volumes | Box plot displaying the distribution of tumor and specimen volumes measures gathered across different stages of the study. |
| Figure 5. Tumor classification       | Bar chart displaying the cases identified as IBD, DCIS or both, and details of subtype classifications for invasive cases. |

|  |                           |                  |                |
|--|---------------------------|------------------|----------------|
|  | Form               | Form Nr.  | 1M-DMST-011-A3 |
|  | Statistical Analysis Plan | Page      | 40 of 116      |
|  |                           | Version # | 0.1            |

**Figure 6.** BREAST-Q scores

Box plot displaying the distribution of BREAST-Q Rasch scores from pre and post operative modules.

